## 2. INTRODUCTION

### 2.1. Background & Rationale

Closure of surgical site incisions in orthopedic spine procedures may include multiple skin layers. Depending on the depth of the incision, suturing of the adipose layer, dermis, subcutaneous, and epidermal layers may be required. Wound closure of the subcutaneous layer may be accomplished by using different modalities such as staples, sutures, or topical skin adhesives. The decision to use one modality over another is largely based on surgeon preference and the area of the body. Topical skin adhesives, such as Opticlose (Medline Industries, LP) and Dermabond (Johnson & Johnson) are ideal for approximating and adjoining opposing skin edges together from lacerations or incisions. This study will evaluate the durability of the Opticlose topical adhesive regarding its ability to hold wound edges together without dehiscence or need for re-approximation following wound closure. The two arms of the study will entail the comparison of participants randomized into either the OptiClose (Secure and Rapid) groups or the Dermabond (Prineo and Advance) groups for the two incision site lengths (incisions large enough to require a combination of mesh and glue or those small enough to require glue only). Recruitment will continue until a minimum of 30 evaluable participants are enrolled and randomized into each group for a particular incision length. In total, 60 participants will be needed to complete the entire study.

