### **6.2 Post-operative Application of Surgical Site Adhesive**

After the completion of the surgical procedure the surgical site will be prepared in a standard fashion using appropriate layered closure. During this time, the products (Opticlose or Dermabond), will be applied to the surgical site incision. Following the application of the products, the time the products take to dry on the surgical site will be recorded using a stopwatch.

For the mesh group, the stopwatch will begin when the package is opened and once the mesh is laid down for initial application. Once the mesh is appropriately applied, the first time stamp will be recorded. The stopwatch will begin again once the glue has been opened and will stop once the glue has sufficiently covered the mesh for a second time stamp. The stopwatch will then start again, and the applicator will touch the application site at 15 second intervals until no glue is detected on the gloved finger. Once dry, the third and final time stamp will be recorded.

For participants assigned to the glue only group, the stopwatch will begin once the glue has been opened and will stop once the target area has been sufficiently covered for the first time stamp. The stopwatch will begin a second time and the applicator will touch the application site at 15 second intervals until no glue is detected on the gloved finger. Once dry, the second time stamp will be recorded.

The number of applicator tubes used when applying the various products will also be recorded during the product application.

Throughout this process, the circulating nurse will be assessing the participants for potential adverse events related to any surgical site infections or any signs of allergic skin

reactions. If an allergic reaction is detected the assessment will include an International Contact Dermatitis Research Group (ICDRG) grading system (see appendix). Following the completion of the assessment, the participants will be allowed to leave and follow up in their next office visits.

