## **8 STATISTICAL CONSIDERATIONS**

### **8.1. Sample Size Determination**

The purpose of this study is to show non-inferiority between the two products. We are reporting superiority results, as the noninferiority results were indeterminate. A sample size of 30 per incisional length group was estimated based on the secondary outcome of difference in mean “Dry Time” using estimated means (no standard deviations) from the vendor for both OptiClose and Competitor product, and estimation of effect size. The comparison will be made using a one-sided, two-sample unequal-variance t-test, with a Type I error rate ( $\alpha$ ) of 0.025. The standard deviation for Group 1 is assumed to be 0.01 and the standard deviation for Group 2 is assumed to be 0.01. With sample sizes of 15 in OptiClose Product and 15 in Dermabond, and with 90% power, the corresponding detectable difference in means is 0.02226. Provided exact standard deviations, an exact difference can be adjusted accordingly. The detectable difference was computed using PASS 2024, version 24.0.2.

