### **Dry Time**

- Dry time down to the closest measure in seconds will be summarized using a mean and standard deviation and will be compared across groups with post-hoc comparison tests. Total time with glue time, mesh time, and dry time will be summarized using a mean and standard deviation.

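### Section 8.1's detectable difference of 0.02226 does not follow from its stated inputs, which give 0.01226, and its unitless SD of 0.01 is not a usable planning value in seconds or minutes

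*Combined protocol and SAP*

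**What the plan says.** Section 8.1 says that the 30 participants per incision-length group were "estimated based on the secondary outcome of difference in mean “Dry Time” using estimated means (no standard deviations) from the vendor". The test is specified: "The comparison will be made using a one-sided, two-sample unequal-variance t-test", with a type I error rate of 0.025. On variability, "The standard deviation for Group 1 is assumed to be 0.01", and the same value is assumed for Group 2. With 15 participants per product the section concludes that, "with 90% power, the corresponding detectable difference in means is 0.02226". No unit accompanies the SD or the difference, and no margin is given, although the section opens with a non-inferiority purpose. It adds that the difference can be adjusted once exact SDs are available.

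Section 6.2 describes the dryness reading: "the applicator will touch the application site at 15 second intervals until no glue is detected on the gloved finger". The Dry Time entry under 8.8.2 says the outcome is "Dry time down to the closest measure in seconds", summarized by mean and SD.

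Section 2.1 says "Recruitment will continue until a minimum of 30 evaluable participants are enrolled and randomized into each group for a particular incision length", and its next sentence gives a total of 60. Section 8.2 has 15 participants per product and 30 per incision-length group, again 60 in all.

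**The concern.** Section 8.1 is the only sample-size justification in the plan, so its detectable difference is what a reader will use to judge what the trial could have shown on dry time. A reader who enters the printed inputs into any standard program gets a different answer. The missing unit makes this worse. Without it, neither 0.01 nor 0.02226 can be compared with an actual dry time, and in the two units a reader would try first the assumed SD is far finer than the 15-second check can register. At stake is whether the 90% power statement can be relied on when the dry-time result is interpreted.

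**Working it through.** **Inputs, all from 8.1.** One-sided unequal-variance t-test; alpha 0.025; SD 0.01 in each group; n = 15 per product; power 90%. Stated result: 0.02226.

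**Attempt to reproduce the stated figure.**

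- Standard error of the difference: 0.01 × √(1/15 + 1/15) = 0.0036515.
- With equal SDs and equal n, the Satterthwaite degrees of freedom are 28, and the one-sided 2.5% critical value is 2.0484.
- The noncentral t with 28 df reaches 90% power at a noncentrality of 3.3588.
- Detectable difference: 3.3588 × 0.0036515 = 0.01226. The normal approximation, 0.0036515 × (1.960 + 1.282), gives 0.01184.

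The stated figure is not reproduced. It is 0.02226 / 0.01226 = 1.8 times the computed one.

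**What 0.02226 would imply under the same inputs.**

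- Noncentrality 0.02226 / 0.0036515 = 6.096, so power is 99.996%.
- 5 per product would give 86.8% power and 6 would give 93.4%.
- For 15 v 15 to have 90% power at 0.02226, the SD would have to be 0.01 × 0.02226 / 0.012264 = 0.01815.

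**Could another input explain it?**

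- With n = 15 and SD 0.01, one- or two-sided alpha from 0.05 to 0.001 and power from 80% to 99.9% did not give 0.02226. The nearest was 0.02205, which needs one-sided alpha 0.005 and 99.9% power.
- SDs of 0.01 and 0.02 give 0.01965; SDs of 0.02 and 0.02 give 0.02453.
- The gap is 0.02226 − 0.01226 = 0.01000. If the test were against a margin or reference value of 0.01, power at 0.02226 would be the power for a shift of 0.01226, which is 90.0%. That fits, but 8.1 states no such value.

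**Scale.** The unit is not given, so each candidate has to be tried against the 15-second check in 6.2.

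- If 15 readings lie on a 15-second grid and just one differs from the rest by one step, the sample SD is 15/√15 = 3.87 s (0.065 min). No smaller non-zero value is possible. It is 387 times 0.01 s and 6.5 times 0.01 min.
- For readings split between two adjacent checks, an SD of 0.6 s requires 15 × √(p(1 − p)) = 0.6, so p = 0.0016. About 99.8% of participants would have to be found dry at the same check.
- A simulation used 15 per product, readings rounded up to the next 15-second check, a random position of the true mean relative to the checks, and the Welch test:

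| Unit assumed | SD | Difference 0.01226 | Power | Difference 0.02226 | Power |
|---|---|---|---|---|---|
| Seconds | 0.01 s | 0.012 s | about 0.1% | 0.022 s | about 0.2% |
| Minutes | 0.6 s | 0.74 s | about 8% | 1.34 s | about 14% |
| Hours | 36 s | 44 s | about 90% | 80 s | above 99.9% |

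In minutes, at the smaller difference, all 30 participants have the same recorded time in about 81% of simulated trials.

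**Scale-free statement.** 0.012264 / 0.01 = 1.2264, so 15 v 15 has 90% power for a difference of 1.23 SD. For illustration, with assumed SDs, that is 1.2264 × 15 = 18.4 s at SD 15 s and 1.2264 × 30 = 36.8 s at SD 30 s.

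**The case against.** The best reply is that the software output may be right and only the write-up incomplete. Section 8.1 has a non-inferiority purpose, and a margin or reference value of 0.01 would give 0.02226. This stands. A reader might infer a one-digit typing error, since the two figures differ in one digit, but the documents support that no better than an omitted input. Replacing the number without checking could turn a correct output into a wrong one.

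A second reply concerns the measurement. A reader might infer from the grid that the SD cannot fall below 15/√12 = 4.33 s, nor the detectable difference below 1.2264 × 4.33 = 5.3 s. Those are not minima. The 4.33 s figure assumes true times spread across the grid. With a true SD of 0.6 s, the recorded SD in a sample of 15 averages only about 0.8 s, because most samples have identical readings. Nor does recording to the second clearly conflict with 6.2: only the last time stamp is on the touch schedule, while mesh and glue times are ordinary stopwatch readings. The simulated powers depend on a guessed unit, and hours would survive the grid, though the documents nowhere use hours for dry time.

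Third, dry time is a secondary outcome, 8.1 openly says no SDs were available, and on the printed inputs 15 v 15 more than covers 0.02226. This is fair: nothing here shows that the trial is too small. But the promise to adjust the difference once SDs are known does not repair a figure that fails under the SDs already assumed.

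Finally, the wording in 2.1 might be read as 30 per product per length, or 120. Its next sentence and 8.2 both settle on 60, so this is a minor ambiguity.

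**Conclusion.** The stated 0.02226 does not follow from 8.1 as written. The printed inputs give 0.01226, and the power at 0.02226 would be 99.996%. This needs no assumption beyond the inputs in the section. Whether a number is wrong or an input is missing cannot be decided from the documents.

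The SD of 0.01 has no unit and no source. If it means seconds or minutes, it is not a usable planning value for a reading taken every 15 seconds. That part rests on the unit being one of those two. An SD close to zero is possible if nearly everyone is found dry at the same check, but that is no basis for planning. What survives without any unit is that 15 v 15 has 90% power for a difference of 1.23 SD. The 90% claim is therefore unsupported on the scale of seconds until a justified SD is supplied.

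**What to change.** Check the software report behind 8.1, then make whichever change it supports:

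- replace 0.02226 by 0.01226;
- correct the SD (about 0.018 in both groups would reproduce 0.02226); or
- state the margin or reference value that was left out.

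In every case, state the unit of the SD and the difference, and say where the SD comes from. Restate the design as 15 v 15 per incision-length group having 90% power for a difference of 1.23 SD, with the detectable difference in seconds over a range of SDs labelled as assumed (for example about 18 s at SD 15 s and 37 s at SD 30 s). If a margin applies, add it to these differences explicitly. In the Dry Time entry of 8.8.2, say which time stamp comes from the 15-second check. Do not present 4.3 s or 5.3 s as lower limits.

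As a minor wording edit, have 2.1 say 15 per product (30 in total) within each incision length, in line with 8.2 and the total of 60.

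The cost is one calculation re-run and short edits to 8.1, 8.8.2 and 2.1, with no extra patients.

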### **8.2 Randomization**

The order of products tested first or second will be randomly assigned according to a randomization table developed by the biostatistics team. We will conduct a two-arm, prospective, unblinded, randomized prospective control trial by which participants will be randomly assigned to either receive treatment A: the Dermabond wound closure adhesive or the treatment B: OptiClose wound closure adhesive in participants undergoing the closure of any subcutaneous tissue following surgical site incisions. After assignment to treatment arm per incisional length requirements, participants will be randomized using

simple randomization, with 15 participants designated to receive Opticlose and 15 to receive Dermabond. Participants will be patients undergoing a skin closure of a full thickness surgical incision. For the products tested in this study, a total of 60 participants will be required to complete the study, 30 in each incisional length group. If a participant is unable to complete the study, the participant will be replaced such that the new participant will be assigned to the randomization cohort of the replaced participant.

Enrollment will continue until the study from the evaluable number of participants (60) is completed.

### **8.3 Populations for Analyses**

The analyses will be performed on the intent to treat (ITT) population which consists of all subjects who have complete data for all time points and secondary endpoints.

No per protocol, safety, or other analyses groups are planned.

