**Description of Study Intervention:**

This prospective study compares the use of OptiClose and Dermabond in the closure of subcutaneous tissue following surgical site incisions. The study has two separate arms. In the first arm, the incision site will large enough to require the use of a mesh, and participants will be randomized into the OptiClose Secure group or the Dermabond Prineo group. In the second arm of the study, the incision site will be small enough not to require a mesh and will use only glue, and participants will be randomized into the OptiClose Rapid group or the Dermabond Advanced group. In both arms of the study, participants will be assessed at three different time points following the surgical procedure: immediately after application following skin closure, and two subsequent visits. These assessments within this study will investigate the cosmesis score, presence of

possible dehiscence or allergic reactions, dry time, and ease of application.

At the conclusion of the final assessment visit (at the end of the final visit), the participants will be dismissed from the study. Participants are free to withdraw from the study, and the principal investigator may also remove the participant if any issues arise that preclude them from continuing.

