### **8.6 Handling of Missing Values**

All missing data will be quantified in the final report and possible biases for any missing data will be reported.

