### **8.7 Statistical Analysis of Study Endpoints**

Statistical analyses will be conducted in SAS® software, Version 9.4 or higher of the SAS System for Windows (Copyright © 2013 SAS Institute Inc.) or other appropriate statistical software.

All continuous variables will be summarized using the following descriptive statistics: n (non-missing sample size), mean, standard deviation, median, maximum and minimum. The frequency and percentages (based on the non-missing sample size) of observed levels will be reported for all categorical measures. In general, all data will be listed, sorted by site, treatment and subject, and when appropriate by visit number within subject. All summary tables will be structured with a column for each treatment in the order (Control, Experimental) and will be annotated with the total population size relevant to that table/treatment, including any missing observations. 95% confidence intervals will be calculated for all means.

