#### **8.8.4 Adverse Device Events**

All adverse device events will be included in the analyses and report documents, including but not limited to skin irritation, redness, and itching.

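### The only analysis set is called ITT but admits complete-data participants only, with non-completers replaced, so entry to the primary and secondary analyses depends on post-randomisation events

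*Combined protocol and SAP*

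**What the plan says.** All references are to the combined protocol and SAP.

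- **Analysis set.** Section 8.3 says that the analyses use the intent-to-treat population, "which consists of all subjects who have complete data for all time points and secondary endpoints". It adds: "No per protocol, safety, or other analyses groups are planned".
- **Replacement.** Section 8.2: "If a participant is unable to complete the study, the participant will be replaced", with the newcomer taking the same randomisation cohort. It also says: "Enrollment will continue until the study from the evaluable number of participants (60) is completed".
- **Removal.** Besides voluntary withdrawal, the synopsis (Description of Study Intervention) provides that "the principal investigator may also remove the participant if any issues arise that preclude them from continuing". Section 8.2 describes the trial as unblinded.
- **Missing data.** Section 8.6: "All missing data will be quantified in the final report and possible biases for any missing data will be reported". For categorical measures, section 8.7 begins "The frequency and percentages (based on the non-missing sample size" and goes on to annotate each table with a total that counts missing observations. Section 8.8.3 plans no supplemental analyses.
- **Adverse device events.** Section 8.8.4: "All adverse device events will be included in the analyses and report documents".
- **Timing.** The Schedule of Activities and section 6.3 place the dehiscence check and the cosmesis score at both follow-up visits.

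**The concern.** An intent-to-treat set is fixed at randomisation. The set in 8.3 is fixed at the end of follow-up, by which records happen to be complete, so it is a completers set under another name.

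Take a participant with dehiscence recorded at Follow-up 1 who then misses Follow-up 2, or who lacks one cosmesis item. The primary outcome is already known to be failure, yet 8.3 excludes the participant from the primary analysis. If the participant cannot complete the study, 8.2 fills the place with someone else. The primary analysis thus depends on post-randomisation events and on secondary data that have no bearing on the primary outcome.

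Section 8.1 states a non-inferiority purpose. Where failures are lost at similar rates from both products, a real deficit of one product shrinks towards zero, which makes a non-inferiority conclusion easier to reach. A report that called this set ITT would also mislead its readers.

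**Working it through.** **Does anything in the plan bring excluded participants back?** Section 8.6 describes missing data but gives no rule for an incomplete primary outcome and no sensitivity analysis. The non-missing denominators of 8.7 leave incomplete participants out again. Sections 8.3 and 8.8.3 rule out further sets and analyses. The provisions of 8.6 and 8.7 would also have little to act on if every analysed participant had complete data, so the sections fit together poorly.

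**Inputs from the plan.** Section 8.2 gives 15 participants per product in each incision-length group, so 2 × 15 = 30 per product and 60 in all. The documents state no failure rate, dropout rate or non-inferiority margin, so there is no figure of the plan's own to reproduce on this point. The sample-size calculation in 8.1 concerns dry time and gives no input here.

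**Assumed inputs.** Let f be the true failure rate, L the probability of incomplete data among failures, and S the same among successes. The expected failure rate in the 8.3 set is

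f(1 − L) / [f(1 − L) + (1 − f)(1 − S)].

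With S = 0:

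| True f | L = 25% | L = 50% | L = 100% |
|---|---|---|---|
| 5% | 3.8% | 2.6% | 0% |
| 10% | 7.7% | 5.3% | 0% |
| 20% | 15.8% | 11.1% | 0% |

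For example, f = 10% and L = 50% give 0.05 / (0.05 + 0.90) = 5.3%.

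**Some successes also incomplete.** With L = 50% and S = 5%, a true 10% appears as 0.05 / (0.05 + 0.855) = 5.5%, and a true 20% as 0.10 / (0.10 + 0.76) = 11.6%.

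**When there is no bias, or the reverse.** With L = S = 10%, a true 10% stays at 10%. With L = 5% and S = 10%, it rises to 0.095 / (0.095 + 0.81) = 10.5%.

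**Effect on the product difference.** Take true failure of 20% against 5%, with S = 0 and the same L for both products. The true difference is 15.0 points. At L = 50% it becomes 11.1 − 2.6 = 8.5 points, and at L = 100% it is 0. If L differs by product, a difference can also be created. With a true 10% for both products, L = 25% for OptiClose and L = 50% for Dermabond give 7.7% against 5.3%, which is 2.4 points against OptiClose.

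**Extreme illustration.** Suppose that 6 of 36 OptiClose participants fail and all 6 are incomplete, against 0 of 30 on Dermabond. Counting everyone gives p = 0.028 (Fisher) or p = 0.019 (uncorrected chi-square). After exclusion and replacement the table reads 0/30 against 0/30.

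**Weight of one participant.** 1/15 = 6.7 points within an incision-length group; 1/30 = 3.3 points if the two groups are pooled. Section 8.8.1 does not say which comparison is meant.

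**Number randomised.** If evaluable means inside the 8.3 set, 60 / (1 − fL) are needed when S = 0. At f = 20% this is 60/0.90, about 67, for L = 50%, and 60/0.80 = 75 for L = 100%.

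**The case against.** The strongest reply is that the mechanism is assumed. No section says that dehiscence, re-approximation or a skin reaction ends participation. A participant whose wound fails but who attends both visits with full records stays in the set. The removal clause in the synopsis is general and is not tied to outcome. Patients who heal well may be the ones who skip a visit, and then the bias runs the other way. All of this stands, and it makes the size and direction of any bias conditional. It does not rescue the definition, because the rule still excludes a known failure whenever a later item is missing.

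Three stronger readings are tempting, and the documents do not support them.

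- A reader might infer that adverse events drop out of every analysis. Section 8.8.4 promises to include all adverse device events, and sections 7.8 and 9.1.2 require reporting and investigator review. What the text shows is a contradiction between 8.3 and 8.8.4.
- A reader might infer that the rule necessarily favours OptiClose. That depends on which product loses more failures. Section 8.1 also says that superiority results are being reported, and for a superiority test a shrunken difference does not automatically help the new product.
- A reader might infer that participants without a skin reaction are excluded because ICDRG grading is done only where applicable. Section 8.8.2 defines grade 0 as no reaction, and the appendix lists a negative result, so the absence of a reaction can be recorded.

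**Conclusion.** The point holds for the primary and secondary endpoint analyses, and 8.3 must be corrected. The population rule is wrong as written, which is more than a missing detail: the sole analysis set carries the ITT label, selects on complete follow-up, and is topped up by replacement. Separately, the absence of a safety set in 8.3 contradicts 8.8.4, and the two must be reconciled.

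The documents do not allow a firm estimate of the bias. Under the assumption that only failures are incomplete, at 25% to 50%, a true 10% failure rate would be reported as 7.7% to 5.3%, and a true 20% as 15.8% to 11.1%. No bias is expected if completeness is unrelated to failure, and the sign can reverse. With groups of 15 or 30 per product, a single excluded failure is enough to move a success rate visibly.

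**What to change.** 1. In 8.3, define ITT as all randomised participants, analysed in the assigned product and incision-length group. Section 6.1 randomises on predicted incision size, so some participants may never have a study-product closure. If they are left out, label the set modified ITT.
2. Keep replaced participants in the analysis and count their replacements as additional.
3. Count any observed dehiscence or re-approximation as a primary failure, whatever is missing later.
4. For other missing primary outcomes, report the available data plus prespecified sensitivity analyses over a range of assumptions. Include a worst case for OptiClose (its missing outcomes counted as failures, those of Dermabond as successes).
5. Add a safety set of everyone who received a product, by product received, so that 8.3 agrees with 8.8.4.
6. Keep the complete-data set as a sensitivity analysis only, under that name.
7. Report the numbers randomised, replaced and excluded, with reasons, by product.
8. Section 8.1 already describes non-inferiority results as inconclusive. If data have been seen, label the change post hoc.

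**Cost.** Revised wording in 8.2, 8.3 and 8.6 and some further tables. The analysed number may exceed 60 and success rates may come out slightly lower. Some replaced participants may have no later outcome data, because the plan does not provide for follow-up after withdrawal; for them the sensitivity analyses in step 4 are the only recourse.

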## **6. STUDY PROCEDURES AND ASSESSMENTS**

### **6.1 Participant Screening and Informed Consent**

The pre-visit may take up to 30 minutes. Study staff will screen potential participants and obtain informed consent during this time as described in Section 5.

Participants will be randomized depending on the predicted incision size. If the incision site is large enough to require the use of the mesh and glue combination, participants will be randomized into the OptiClose Secure group or the Dermabond Prineo group. If the incision site is determined to be small enough that it does not require a mesh, participants will be randomized into the OptiClose Rapid group or the Dermabond Advanced group.

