### **8.4 Protocol Deviations**

The list of protocol deviations will be compiled prior to database lock. All deviations will be reviewed and decisions for handling each of the deviations will be made prior to the start of data analysis.

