### **8.8.1 Primary Endpoint**

Incidence of wound edge apposition without dehiscence or need of re-approximation following wound closure.

Counts will be collected of participants not requiring wound re-approximation for both Opticlose and Dermabond. A Chi-Square test will be used to compare the observed frequencies of adverse events between the two products. The test statistic is calculated by comparing the observed frequency to the expected frequency under the null hypothesis. The p-value will be obtained to determine the statistical significance of the observed difference.

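### The stated purpose is non-inferiority, but the only analysis set is a complete-case set labelled ITT, with no as-randomised set and no supportive per-protocol or as-treated safety analysis

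*Combined protocol and SAP*

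**What the plan says.** Section 8.1 opens with "The purpose of this study is to show non-inferiority between the two products" and continues "We are reporting superiority results, as the noninferiority results were indeterminate". No margin or non-inferiority decision rule appears for any endpoint. Section 8.8.1 tests the primary endpoint for a difference: "A Chi-Square test will be used to compare the observed frequencies of adverse events between the two products".

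Section 8.3 names one analysis set, the "intent to treat (ITT) population which consists of all subjects who have complete data for all time points and secondary endpoints", and closes with "No per protocol, safety, or other analyses groups are planned". Section 8.8.3 lists no supplemental analysis.

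Four other places bear on who is analysed, and as what:
- Section 6.1: "Participants will be randomized depending on the predicted incision size".
- Section 8.2: the trial is unblinded, with 15 participants per product in each incision-length group. When someone cannot finish, "the participant will be replaced such that the new participant will be assigned to the randomization cohort of the replaced participant".
- Section 8.4: "All deviations will be reviewed and decisions for handling each of the deviations will be made prior to the start of data analysis". It gives no rule for a participant who received a product other than the one assigned.
- Section 8.8.4: all adverse device events are included, without saying whether they are tabulated by assigned or received product.

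The documents do not say whether participants are analysed as assigned or as treated.

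**The concern.** In a superiority trial, departures from assignment usually shrink the observed difference, so an as-randomised analysis errs on the safe side. In a non-inferiority trial the same shrinkage works in favour of the claim. It is therefore usual to set a per-protocol analysis beside the as-randomised one, so that a reader can see whether a 'not worse' result owes anything to departures from assignment.

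This plan states a non-inferiority purpose and rules that comparison out. Nor does it have a true as-randomised set to compare with. The set called ITT excludes participants after randomisation for incomplete data, but retains anyone with complete data whatever product they received. It is neither as-randomised nor per-protocol. At stake is how far a 'not worse' statement about wound apposition could be trusted and, for safety, whether skin reactions are attributed to the product that was on the skin.

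**Working it through.** **1. The plan's own figures.** The plan gives no figure on this point. The one calculated figure in 8.1, a detectable dry-time difference of 0.02226, concerns sizing. From the stated inputs (15 per arm, SD 0.01, one-sided 0.025, 90% power) the noncentral t gives 0.01226. That mismatch is a separate matter, and nothing below uses the figure.

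**2. Inputs for an illustration.**

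| Input | Value | Source |
|---|---|---|
| n per arm | 15 within a length group | Section 8.2 |
| n per arm if length groups are pooled | 15 + 15 = 30 | Arithmetic; pooling is not specified |
| One-sided error rate | 0.025 | Section 8.1, stated there for dry time only |
| Margin M | 15 points | Assumed |
| True failure, OptiClose v Dermabond | 20% v 5%, exactly at the margin | Assumed |
| Share c of each arm receiving the other brand | 0, 10%, 20% | Assumed, symmetric |

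**3. Formula.** Analysed as assigned, the apparent failure rates are p1 = 0.20 − 0.15c and p2 = 0.05 + 0.15c, so the apparent difference is 0.15(1 − 2c). With SE = √{[p1(1 − p1) + p2(1 − p2)]/n}, the chance that the upper 97.5% limit falls below M is approximately Φ(0.30c/SE − 1.96).

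**4. Results.**

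| n per arm | c | p1, p2 | SE | 0.30c/SE | False non-inferiority |
|---|---|---|---|---|---|
| 15 | 0 | 0.200, 0.050 | 0.1176 | 0 | 2.5% |
| 15 | 10% | 0.185, 0.065 | 0.1188 | 0.253 | 4.4% |
| 15 | 20% | 0.170, 0.080 | 0.1196 | 0.502 | 7.2% |
| 30 | 0 | 0.200, 0.050 | 0.0832 | 0 | 2.5% |
| 30 | 10% | 0.185, 0.065 | 0.0840 | 0.357 | 5.5% (0.0545) |
| 30 | 20% | 0.170, 0.080 | 0.0846 | 0.709 | 10.6% (0.1055) |

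One swap in each arm of 15 (c = 6.7%) gives 3.7%.

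**5. A milder pattern.** Suppose only OptiClose-assigned participants receive the other brand. Exact binomial enumeration was run with a Newcombe lower limit, assuming Dermabond success of 90% to 95%, margins of 10 to 25 points and a true difference equal to the margin. With 15 per arm the false non-inferiority rate is 1.6% to 2.9% with no switch, 1.8% to 3.7% with one, 2.0% to 4.6% with two and 2.3% to 5.8% with three. With 30 per arm it is 1.6% to 3.0% with none and 2.1% to 5.0% with three. The direction is the same and the size is modest.

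**6. What a misjudged incision size does.** Assignment follows predicted size (6.1). A participant moved from mesh to glue only could go from OptiClose Secure to OptiClose Rapid, or from Dermabond Prineo to Dermabond Advanced. If the brand is kept, the OptiClose–Dermabond contrast is not diluted and the formula above does not apply. The participant is nevertheless outside the assigned product and length group, and 8.3 does not say in which comparison to count them.

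**7. Whether the existing set removes switched participants.** It does not. Completeness of data is the only criterion in 8.3, so a participant given the other product and followed to the last visit stays in. One who received the assigned product but lacks a single secondary endpoint drops out.

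**The case against.** The strongest reply is that a false non-inferiority finding is not an output of this plan. No margin or decision rule exists, the primary test is for a difference, and 8.1 says superiority is reported because non-inferiority was indeterminate. For a test of difference, dilution makes a false positive less likely. This stands, and it limits the urgency. It does not remove the point: 8.1 still gives non-inferiority as the purpose, and its reference to indeterminate non-inferiority results implies that such an analysis was made.

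A reader might infer that brand switches are likely here because randomisation uses predicted incision size. The documents do not support that. They describe one application of product per participant, mention no brand switching and give no rate. A size mismatch need not change the brand. A reader might also take the set to be a genuine as-randomised analysis that merely lacks a companion, but 8.3 defines it as a complete-case set and 8.2 replaces those who do not finish.

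It can also be said that 8.4 already provides a check, because deviations are listed before database lock and their handling is decided before analysis. This is a partial answer. No criteria are given, and in an unblinded trial case-by-case decisions can be made with knowledge of both product and outcome.

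Finally, the sizes in the working rest on assumed inputs. With no switches, a per-protocol set changes nothing on this point.

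**Conclusion.** The concern holds in a limited form. The analysis sets do not suit the stated purpose: the only set is a mislabelled complete-case set, no rule says participants are analysed as assigned, and per-protocol and safety sets are expressly excluded. Any brand switching analysed as assigned would favour a non-inferiority reading and would be conservative for the superiority test.

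Under the assumed margin, failure rates and symmetric switching of 10% or 20%, the false non-inferiority rate goes from 2.5% to 4.4% or 7.2% at the 15 per arm of a single length group. The 5.5% and 10.6% at 30 per arm require pooling that the plan does not specify. A few one-way switches have a smaller effect. These figures show direction and order of magnitude; they do not estimate an error in this trial. The change is worth making because it is cheap, but a per-protocol set cannot supply the missing margin.

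**What to change.** In section 8.3:

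- Redefine the ITT set as all randomised participants, analysed in the product and length group to which they were assigned, including those later replaced. Remove the complete-data condition. State how a missing primary outcome is handled, since 8.6 only says that missing data will be quantified.
- Replace the last sentence with a per-protocol set: randomised participants who received the assigned product in the assigned length group, without a major deviation, with the list fixed before outcome data are summarised. Use it for a supportive analysis of the primary endpoint, reported beside the as-randomised result. Discuss any disagreement when interpreting a 'not worse' conclusion.
- Tabulate skin reactions and adverse device events by product actually received.

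Do not make a non-inferiority claim conditional on the two sets agreeing. That would turn a supportive analysis into a co-primary one, and agreement has no definition without a margin. If non-inferiority is no longer the aim, 8.1 should say so plainly.

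The cost is two definitions, a missing-data rule and one repeated analysis. The downside is that a per-protocol estimate can carry selection bias, which is why it should remain supportive.
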